Appendix D. Optional Exploratory Research and Validation Studies – Schedule of Activities

Activity	Period A							Period B				Period C			
	Screening (Day -30 to Day -7)	Baseline (Day 1)	Wk 2	Wk 4	Wk 8	Wk 12	Wk 13	Wk 14	Wk 15	Wk 17	Wk 20	Wk 24 or Premature Discontinuation Visit	Unscheduled Study Visit	70-Day Call	
Informed Consent for Exploratory Research and Validation Studies ^a	X														
Pharmacogenetic Sample ^{a,b}		X													
Epigenetic Sample ^{a,b}		X	X			X				X		X			
Transcriptomic Sample ^{a,b}		X	X			X				X		X			
Serum and Plasma ^{a,b}		X	X			X				X		X			
Peripheral Blood Mononuclear Cells ^{a,b}		X	X			X				X		X			
Microbiome Swab ^{a,b}		X	X			X				X		X			
Surgical Resection Punch Biopsies ^{a,b}							X								
Skin Punch Biopsies ^{a,b}		X				X ^c						X			

- a. Subjects must sign and date the separate informed consent before any of these optional exploratory research and validation studies samples may be collected (see Section 9.3).
A subject may participate in the main study whether or not that subject volunteers to the collection of these optional samples.
- b. Blood and tissue samples must be obtained prior to dosing.
- c. Collected only from subjects who will not undergo surgery.

Appendix E. Lesion Counts – Sample

Lesion Counts ^a	Abscess	Non-Draining Fistula	Draining Fistula	Non-Inflammatory Nodule	Inflammatory Nodule	Hypertrophic Scar	Longest Distance (mm) Between 2 Relevant Lesions ^b	Intervening Normal Appearing Tissue (Yes or No) ^c
Left Axilla								
Right Axilla								
Left Sub/inframammary Area								
Right Sub/inframammary Area								
Intermammary Area								
Left Buttock								
Right Buttock								
Left Inguino-crural Fold ^d								
Right Inguino-crural Fold ^d								
Perianal								
Perineal								
Other								
Totals								

- a. Lesion counts are to be recorded at every Study Visit in Period A and Period C.
- b. If only 1 lesion, record diameter of that single lesion.
- c. Are all lesions in this area clearing separated by normal appearing tissue? Answer: 'Yes' or 'No'
- d. Includes the immediate adjacent area.

Appendix F. Dermatology Life Quality Index (DLQI) – Example

The aim of this questionnaire is to measure how much your skin problem has affected your life OVER THE LAST WEEK. Please check one box for each question.

Question	Response	
1. Over the last week, how itchy, sore, painful or stinging has your skin been?	Very much  A lot  A little  Not at all 	
2. Over the last week, how embarrassed or self-conscious have you been because of your skin?	Very much  A lot  A little  Not at all 	
3. Over the last week, how much has your skin interfered with you going shopping or looking after your home or yard ?	Very much  A lot  A little  Not at all 	Not relevant 
4. Over the last week, how much has your skin influenced the clothes you wear?	Very much  A lot  A little  Not at all 	Not relevant 
5. Over the last week, how much has your skin affected any social or leisure activities?	Very much  A lot  A little  Not at all 	Not relevant 
6. Over the last week, how much has your skin made it difficult for you to do any sport ?	Very much  A lot  A little  Not at all 	Not relevant 

7. Over the last week, has your skin prevented you from working or studying ? If "No," over the last week how much has your skin been a problem at work or studying ?	Very much  A lot  A little  Not at all 	Not relevant 
8. Over the last week, how much has your skin created problems with your partner or any of your close friends or relatives ?	Very much  A lot  A little  Not at all 	Not relevant 
9. Over the last week, how much has your skin caused any sexual difficulties ?	Very much  A lot  A little  Not at all 	Not relevant 
10. Over the last week, how much of a problem has the treatment for your skin been, for example by making your home messy, or by taking up time?	Very much  A lot  A little  Not at all 	Not relevant 

Please check you have answered EVERY question. Thank you.

©AY Finlay, GK Khan, April 1992, This must not be copied without the permission of the authors.

Appendix G. EuroQoL EQ-5D – Example

By placing a checkmark in one box in each group below, please indicate which statements best describe your own health state today.

Mobility

- I have no problems in walking about
- I have some problems in walking about
- I am confined to bed

Self-Care

- I have no problems with self-care
- I have some problems washing or dressing myself
- I am unable to wash or dress myself

Usual Activities (*e.g., work, study, housework, family or leisure activities*)

- I have no problems with performing my usual activities
- I have some problems with performing my usual activities
- I am unable to perform my usual activities

Pain/Discomfort

- I have no pain or discomfort
- I have moderate pain or discomfort
- I have extreme pain or discomfort

Anxiety/Depression

[figure not shown]
- I am not anxious or depressed
- I am moderately anxious or depressed
- I am extremely anxious or depressed

©1998 EuroQol Group. EQ-5D™ is a trade mark of the EuroQol Group.

To help people say how good or bad a health state is, we have drawn a scale (rather like a thermometer) on which the best state you can imagine is marked 100 and the worst state you can imagine is marked 0.

We would like you to indicate on this scale how good or bad your own health is today, in your opinion. Please do this by drawing a line from the box below to whichever point on the scale indicates how good or bad your health state is today.

**Your own
health state
today**

Appendix H. Hidradenitis Suppurativa Impact Assessment – Example

Instructions: This questionnaire includes 18 questions about the impacts that you may experience associated with your Hidradenitis Suppurativa (HS). Hidradenitis Suppurativa is a skin condition that affects areas with sweat glands such as the underarms, breasts, inner thighs, groin, and buttocks. People often refer to their HS as boils, cysts, or lesions on their skin.

Please clearly mark an **"x" in the box ()** that best describes how you have been affected by your **HS** in the **past 7 days**. There are no right or wrong answers to any of the questions.

[Example of HSIA in process of being reformatted for this protocol.]

Appendix I. Hidradenitis Suppurativa Patient's Global Assessment of Skin Pain – Example

Please answer the questions below before you go to bed.

Please mark an "X" in the box that best describes the severity of your skin pain in the last 24 hours.

No skin pain											Worst skin pain ever
0	1	2	3	4	5	6	7	8	9	10	

In the last 24 hours, mark an "X" in the box that best describes your skin pain on average due to your HS.

No skin pain											Worst skin pain ever
0	1	2	3	4	5	6	7	8	9	10	

Appendix J. Hidradenitis Suppurativa Patient Global Impression Change – Example

1. Since your last visit, how would you rate your pain due to your Hidradenitis Suppurativa (HS)?
 - Very much worse
 - Much worse
 - A little worse
 - No change
 - A little better
 - Much better
 - Very much better

Appendix K. Hidradenitis Suppurativa Symptom Assessment – 7 Day Recall – Example

Instructions: This questionnaire includes nine questions about the symptoms you may experience associated with your Hidradenitis Suppurativa (HS). Hidradenitis Suppurativa is a skin condition that affects areas with sweat glands such as the underarms, breasts, inner thighs, groin, and buttocks. People often refer to their HS as boils, cysts, or lesions on their skin.

Please clearly mark an "x" in the box (☒) that best describes how severe your HS symptoms were over the **past 7 days**. There are no right or wrong answers to any of the questions.

1. Over the **past 7 days**, what was the worst pain you felt in the area(s) affected by your HS?

No pain at all Extreme pain

▼ ▼

0 1 2 3 4 5 6 7 8 9 10

☐ ☐ ☐ ☐ ☐ ☐ ☐ ☐ ☐ ☐ ☐

2. Over the **past 7 days**, what was the worst drainage you had in the area(s) affected by your HS?

No drainage at all Extreme drainage

▼ ▼

0 1 2 3 4 5 6 7 8 9 10

☐ ☐ ☐ ☐ ☐ ☐ ☐ ☐ ☐ ☐ ☐

3. Over the **past 7 days**, how red was your skin in the area(s) affected by your HS?

[figure not shown]
Not red at all Extremely red

▼ ▼

[figure not shown]
0 1 2 3 4 5 6 7 8 9 10

☐ ☐ ☐ ☐ ☐ ☐ ☐ ☐ ☐ ☐ ☐

4. Over the **past 7 days**, how tender was your skin in the area(s) affected by your HS?

[figure not shown]

5. Over the **past 7 days**, how swollen was your skin in the area(s) affected by your HS?

[figure not shown]

6. Over the **past 7 days**, how hard did your skin feel in the area(s) affected by your HS?

[figure not shown]
Note: Please do not consider any hardness that you may have from the scars left on your skin from HS.

[figure not shown]
7. Over the **past 7 days**, how hot was your skin in the area(s) affected by your HS?

8. Over the **past 7 days**, how bad was the smell coming from the area(s) affected by your HS?

9. Over the **past 7 days**, how itchy was your skin in the area(s) affected by your HS?

Appendix L. Short Form-12 – Example

[Sample not available, licensing in process.]

Appendix M. Treatment Satisfaction Questionnaire for Medication – Example

TSQM (Version 1.4)

Treatment Satisfaction Questionnaire for Medication

Instructions: Please take some time to think about your level of satisfaction or dissatisfaction with the medication you are taking in this clinical trial. We are interested in your evaluation of the effectiveness, side effects, and convenience of the medication *over the last two to three weeks, or since you last used it*. For each question, please place a single check mark next to the response that most closely corresponds to your own experiences.

1. How satisfied or dissatisfied are you with the ability of the medication to prevent or treat your condition?

- O₁ Extremely Dissatisfied
- O₂ Very Dissatisfied
- O₃ Dissatisfied
- O₄ Somewhat Satisfied
- O₅ Satisfied
- O₆ Very Satisfied
- O₇ Extremely Satisfied

2. How satisfied or dissatisfied are you with the way the medication relieves your symptoms?

- O₁ Extremely Dissatisfied
- O₂ Very Dissatisfied
- O₃ Dissatisfied
- O₄ Somewhat Satisfied
- O₅ Satisfied
- O₆ Very Satisfied
- O₇ Extremely Satisfied

3. How satisfied or dissatisfied are you with the amount of time it takes the medication to start working?

- O₁ Extremely Dissatisfied
- O₂ Very Dissatisfied
- O₃ Dissatisfied
- O₄ Somewhat Satisfied
- O₅ Satisfied
- O₆ Very Satisfied
- O₇ Extremely Satisfied

**Appendix N. Work Productivity and Activity Impairment Questionnaire:
Specific Health Problem – Example**

The following questions ask about the effect of your hidradenitis suppurativa on your ability to work and perform regular activities. Please fill in the blanks or circle a number, as indicated.

1. Are you currently employed (working for pay)? _____ NO ____ YES

If NO, check "NO" and skip to question 6.

The next questions are about the **past 7 days**, not including today.

2. During the past seven days, how many hours did you miss from work because of problems associated with your hidradenitis suppurativa? *Include hours you missed on sick days, times you went in late, left early, etc. because of your hidradenitis suppurativa. Do not include time you missed to participate in this study.*

_____ HOURS

3. During the past seven days, how many hours did you miss from work because of any other reason, such as vacation, holidays, time off to participate in this study?

_____ HOURS

4. During the past seven days, how many hours did you actually work?

_____ HOURS (*If "0," write "0" and skip to question 6.*)

5. During the past seven days, how much did hidradenitis suppurativa affect your productivity while you were working?

Think about days you were limited in the amount or kind of work you could do, days you accomplished less than you would like, or days you could not do your work as carefully as usual. If hidradenitis suppurativa affected your work only a little, choose a low number. Choose a high number if hidradenitis suppurativa affected your work a great deal.

Hidradenitis suppurativa had no effect on my work	_____	Hidradenitis suppurativa completely prevented me from working
	0 1 2 3 4 5 6 7 8 9 10	
	CIRCLE A NUMBER	

6. During the past seven days, how much did hidradenitis suppurativa affect your ability to do your regular daily activities, other than work at a job?

By regular activities, we mean the usual activities you do, such as work around the house, shopping, child care, exercising, studying, etc. Think about times you were limited in the amount or kind of activities you could do and times you accomplished less than you would like. If hidradenitis suppurativa affected your activities only a little, choose a low number. Choose a high number if hidradenitis suppurativa affected your activities a great deal.

Hidradenitis suppurativa had no effect on my daily activities	_____	Hidradenitis suppurativa completely prevented me from doing my daily activities
	0 1 2 3 4 5 6 7 8 9 10	
	CIRCLE A NUMBER	

WPAI:SHP (US English)

Appendix O. Clinical Study Site Personnel – Study Drug Dispensing Table

Visit	Dose	Dispense Study Drug for Weeks**	Number of Syringes Used Day of Visit	Number of Kits and Syringes per Kit Dispensed for Between Visits
Baseline	160 mg (1st loading dose)	Week 1 (D1 or split over D1+D2)	4 (or 2 if split on two days)	2 kits (4 syringes)
Week 2	80 mg (2nd loading dose)	Week 2 (Day 15) 40 mg/week	2	1 kit (2 syringes)
Week 4	40 mg/week	Weeks 4, 5, 6 and 7	1	2 kits (4 syringes)
Week 8	40 mg/week	Weeks 8, 9, 10, and 11	1	2 kits (4 syringes)
Week 12	40 mg/week	Weeks 12, 13, 14 and 15	1	2 kits (4 syringes)
Week 15	40 mg/week	Weeks 16 and 17	1	1 kit (2 syringes)
Week 17	40 mg/week	Weeks 18, 19, 20 and 21	1	2 kits (4 syringes)
Week 20	40 mg/week	Weeks 22, and 23	1	2 kits (4 syringes) resulting in 1 kit/2 PFS* left over at study's end which should be destroyed if not being used as replacement.

* PFS = Pre-filled syringes.

** Study Investigators will ensure that enough study drug is dispensed at each visit to cover the subject until their next visit.

Appendix P. Subject Injection Instructions – Example Pre-Filled Syringe

1. You will not administer injections to yourself at home on clinic visit days. You or your helper will be taught on a clinic visit day how to give injections subcutaneously (under the skin, not in the muscle) and you will be asked to show the study staff you or your helpers ability to self-inject in the clinic.
2. You will administering injections at home on Day 2 of Week 0 (if directed by your study doctor), on the first day of Weeks 5, 6, 7, 9, 10, 11, (ask your study doctor about Weeks 13 and 14), and on the first day of Weeks 16, 18, 19, 21, 22 and 23 (last dose).
3. Check your dosing chart to make sure you are giving yourself the injection on the same day of the week as your last injection and check the location of the last injection on your home chart so you choose a different location for the current injection
4. Remove your carton from the refrigerator and remove **one** pre-filled syringe (there will be two syringes in the carton). Put the other syringe (syringe 2) back in the carton and place the carton back in the refrigerator.
5. If your pre-filled syringe accidentally becomes frozen, do not use the syringe and contact your study doctor.
6. Prepare a clean area where you will not be distracted.
7. You may self-administer your injection or have a helper, someone who has been approved by the study staff, do so.
8. Check the syringe to make sure the fluid in the syringe is clear and colorless. If you notice anything unusual about the pre-filled syringe, such as the liquid is cloudy, discolored or has flakes in it or the syringe itself doesn't look right to you, contact your study doctor before administering your injection. If there is a question or something unusual suspected by your study doctor, you may be required to return the carton with the full liquid amount in the syringe to your study doctor if requested to do so.

9. Wash your hands with soap and warm water or have your helper do the same. Clean medical gloves are not necessary but may be preferred by your helper.
10. If you or your helper is ready to administer your injection, have your alcohol swab, sharps container (a safe place to put your used syringes) and gauze or cotton ball ready.
 - a. As you or your helper was taught in the clinic, you will first swab the area with alcohol, being careful to go from the inside out in a circular motion, trying not to put alcohol on the same area of your skin twice.
 - b. You will pinch together about 1 inch of skin on either side of your stomach or your upper thighs, remove the needle cap (do not try to put the cap back on after your injection) and stick the needle in with the needle slightly sideways at an angle as shown (see the pictures below).
 - c. Pull back slightly on the plunger.
 - d. If blood does not appear push the plunger until all of the liquid is gone.
 - e. If blood appears in the syringe it means the tip of the needles has entered a blood vessel. Do not begin the injection of the liquid. Pull the needle out of the skin and dispose of that pre-filled syringe.
 - f. Repeat the step 10 to choose and clean a new injection site. Do not use the same syringe; instead use a new pre-filled syringe (syringe 2).

[figure not shown]
11. Remove the syringe and apply pressure with a cotton ball to the injected area.
12. Immediately put the used syringe in your sharps container.

13. Please return all used and unused syringes and empty boxes to the clinic on your next visit.

14. If an injection is missed or something occurs where the full dose cannot be injected, contact your study doctor immediately for further instructions. Please record any missed doses on your subject dosing sheet.
15. Remember to complete your dosing sheet after each injection and to call the study doctor if you are having problems administering your study medication.

Sample Home Chart for Injections

Avoid the area around your navel (belly button), and rotate your weekly injections, see examples 1-4 and start over after 4 injections

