Period B: A 2-week double-blind, placebo-controlled treatment period consisting of Weeks 13 and 14 (the peri-operative period) in which subjects will continue the treatment on the first day of Weeks 13 and 14. The designated surgeon will measure the surface area of the actual surgery and record in source document. Surgery will occur during Week 13. The surgery and post-operative management (e.g., hospitalisation, surgical wound care) will be as per local practice.

[figure not shown]
Period C: A 10-week double-blind, placebo-controlled post-operative treatment period will occur from Week 15 through Week 24, during which the subject will continue the treatment assigned at Day 1 from Week 15 through Week 23. No study drug will be administered at Week 24, the final study visit. Subjects may begin commercial product (as prescribed by the subject's physician) after all Week 24 procedures have been completed.

Study procedures throughout the study are listed in [Appendix C](#). Safety and efficacy measurements will be performed throughout the study as described in Section 5.3.1.

The study visit window will be ± 3 days for the Week 2 and Week 4 visits and ± 7 days, relative to Baseline, for all study visits from Week 8 through Week 24. Surgery takes place at Week 13 after all Week 12 evaluations are completed. A subject will be brought back to the original visit schedule (calculated from the Baseline visit [Day 1]) if the subject is out of the visit window.

Subjects may discontinue adalimumab treatment at any time during study participation. Subjects that end study participation early will have a Premature Discontinuation Visit unless consent to participate is withdrawn.

Figure 1. Study Schematic

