5.5.4 Selection and Timing of Dose for Each Subject

Subjects should take study medication as outline in Section 5.5.1.

At the Baseline visit, after all assessments have been completed, subjects in Arm 1 will receive four injections of active study drug (40 mg/0.8 mL each) and subjects in Arm 2 will receive four placebo injections (0.8 mL each) as detailed in Section 5.5.1.

Appropriate study site personnel will train and then supervise the subject or designee administering at least one injection of the study drug to ensure proper understanding of injection technique (Appendix P). The subject or designee will subsequently dose and be witnessed by study site personnel during their study visits to ensure continued proper technique. When study drug is administered at the Day 1 (Week 0) and Week 2 study visits (see Appendix C), the subject should remain at the study site for approximately 15 to 30 minutes after injection for observation.

For home administration of injection, subjects or qualified designee will be instructed to inject study medication on the same day of the week as their Baseline visit day as detailed in Section 5.5.1. Every kit contains 2 syringes each.

If a subject should forget to administer the injection of study medication on their regularly scheduled dosing date, the subject should take the forgotten injection as soon as she/he remembers the dose was missed up to the day before the next scheduled dose. The subject should not administer two doses on the same day.

Doses not administered (e.g., not taken before the next dose is scheduled), should be recorded as not taken in the source. The extra dose should be returned in its entirety to the study site at the subject's next study visit. Meanwhile, the subject should resume their regular dosing schedule based on the first dosing date at Baseline (Day 1).

In the event the incorrect dose is taken, the entire volume of study drug is not injected, or a dose is missed, the subject should be instructed to contact the study site to determine how to proceed with dosing. The subject must record all dosing information on the Subject-Dosing Diary Sheet.

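### Appendix P step 3 ties home injections to the weekday of the last injection, while Section 5.5.4 and Appendix P step 2 tie them to the Baseline schedule; the dates part after an in-window clinic dose on another weekday

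*Protocol*

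**What the plan says.** Three instructions in the protocol set the date of a home injection.

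- **Section 5.5.4.** Subjects are to "inject study medication on the same day of the week as their Baseline visit day". After a dose that was not taken, the section returns them to the schedule counted from Day 1.
- **Appendix P, step 2.** Home injections fall on the first day of listed study weeks (Weeks 5, 6, 7, 9, 10 and 11 before Week 12). For Weeks 13 and 14 the subject is told to ask the study doctor.
- **Appendix P, step 3.** The subject is to check the dosing chart and "make sure you are giving yourself the injection on the same day of the week as your last injection".

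Two further provisions let these separate. Section 5.1.1 allows visits to move by 3 days either way at Weeks 2 and 4, and by 7 days either way "relative to Baseline, for all study visits from Week 8 through Week 24". Section 5.5.1 and Appendix P step 1 put the dose on a visit day in the clinic, not at home.

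**The concern.** The weekday of the last injection and the weekday of the Baseline visit are the same only while every dose has fallen on the Baseline weekday. A visit inside its window can break that with no missed dose and no departure from the protocol. The subject then holds a sheet whose steps 2 and 3 can name different days, and site staff work from a section that agrees with only one of them.

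What is at stake is the spacing of weekly doses and the meaning of the pre-dose drug-level samples. Section 5.3.5 summarises trough concentrations by time point and plans a within-subject comparison before and after surgery. A trough taken 4 days after the last dose is not the same quantity as one taken 7 days after.

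**Working it through.** **Inputs**

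- Day numbering: Section 5.5.1 sets Week 2 = Day 15 and Week 4 = Day 29, so Week k = Day 7k + 1. This gives Week 5 = Day 36, Week 8 = Day 57, Week 9 = Day 64 and Week 12 = Day 85.
- Windows: ±3 days at Week 4 and ±7 days at Week 8 (Section 5.1.1). Week 2 does not matter here, because the next dose after it is the Week 4 clinic dose.
- s = shift of the clinic visit, in days, from its nominal day (negative = early).

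**Formulas**, for a clinic dose at Week k on Day 7k + 1 + s:

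- Section 5.5.4, and step 2 if weeks run from Day 1: next home dose on Day 7(k + 1) + 1, a gap of 7 − s days.
- Step 3, read as one week after the last injection: next home dose on Day 7k + 1 + s + 7, a gap of 7 days.
- Difference, step 3 minus Section 5.5.4: s days.

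| Clinic dose | s | Clinic day | Section 5.5.4 / step 2 (gap) | Step 3 (gap) | Difference |
|---|---|---|---|---|---|
| Week 4 | −3 | 26 | Day 36 (10) | Day 33 (7) | −3 |
| Week 4 | 0 | 29 | Day 36 (7) | Day 36 (7) | 0 |
| Week 4 | +3 | 32 | Day 36 (4) | Day 39 (7) | +3 |
| Week 8 | −6 | 51 | Day 64 (13) | Day 58 (7) | −6 |
| Week 8 | +3 | 60 | Day 64 (4) | Day 67 (7) | +3 |
| Week 8 | +6 | 63 | Day 64 (1) | Day 70 (7) | +6 |

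With no shift the rules agree. A shift of exactly 7 days either way keeps the weekday, so it is left out. The Week 15, 17 and 20 visits also have a 7-day window and are followed by home doses, so the same formulas apply there.

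**Effect on a trough sample.** Take a Week 8 visit on Day 60 (3 days late) and a Week 12 visit on time, on Day 85.

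- Section 5.5.4: home doses on Days 64, 71 and 78. The Week 12 pre-dose sample comes 85 − 78 = 7 days after the last dose.
- Step 3: home doses on Days 67, 74 and 81. The sample comes 85 − 81 = 4 days after the last dose.

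For a Week 8 visit that is s = 1 to 6 days late and a Week 12 visit on time, the last home dose under step 3 is on Day 78 + s. The interval is then 7 − s, or 6 down to 1 day, against 7 days under Section 5.5.4.

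**Dose count.** With the Week 8 dose on Day 63 (s = 6), Section 5.5.4 gives Days 64, 71 and 78, and step 3 gives Days 70, 77 and 84. That is three home doses before Day 85 either way.

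**The case against.** The best defence is that the hand-out as a whole does not adopt the last-injection rule. Step 2 sets the schedule and agrees with Section 5.5.4, so the fault lies in one clause of step 3, in an appendix headed as an example. Step 3 also begins by sending the subject to the dosing chart. If that chart (Appendix Q) prints fixed dates, they may settle the matter; its content was not available to check. The off-weekday dose is watched by site staff, who could state the next date. All of this stands and limits the weight of the point. It does not remove the conflict: step 3 states its own rule, and Section 5.5.4 refers to Appendix P for injection training.

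On the drug-level data, Section 5.5.6 has injection dates and times recorded, and the population model in Section 8.4 uses actual sampling times. That protects the model. It does not protect the descriptive trough summaries by visit. The windows already vary the dosing interval by themselves, so the conflict adds to variation that is there anyway.

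A reader might also infer a clash over missed doses. Section 5.5.4 lets a subject "take the forgotten injection as soon as she/he remembers the dose was missed up to the day before the next scheduled dose", while Appendix P step 14 says: "If an injection is missed or something occurs where the full dose cannot be injected, contact your study doctor immediately for further instructions". But Section 5.5.4 also sends a subject with a missed dose to the site, and taking a forgotten dose is compatible with making that call. The documents do not support a contradiction there.

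**Conclusion.** The point holds as an internal conflict in the protocol. Appendix P step 3 disagrees with Section 5.5.4 and with step 2 of the same hand-out after an in-window clinic dose off the Baseline weekday. The next home injection date differs by up to 3 days after Week 4 and up to 6 days after Week 8. In the worked case, the time from last dose to the Week 12 sample is 4 days under step 3 and 7 under Section 5.5.4.

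This rests on two readings: study weeks run from Day 1, and step 3 means one week after the last injection. How often it would occur is unknown, because the documents give windows and not visit adherence.

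Three stronger conclusions are tempting but not supported.

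- **Fewer or more doses before Week 12.** In the 6-days-late case the count is three home doses under both rules, and step 2 fixes which weeks are dosed at home.
- **Recorded dosing deviations.** The reportable list in Section 7.0 covers the wrong drug or an incorrect dose and does not name the injection day.
- **Harm to the efficacy result.** Both arms get the same blinded instructions, and no effect on HiSCR (the primary response measure), alpha or power is shown.

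Severity is low. Which dosing-day rule is right is a clinical matter and is not judged here.

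**What to change.** Reconcile Appendix P step 3 with step 2 and Section 5.5.4, so that one rule sets the next home injection date after a clinic dose off the Baseline weekday. The sponsor's clinical team chooses the rule. State in step 2 or Section 5.5.4 that study weeks are counted from Day 1, if that is what is meant. Check that the Appendix Q dosing chart follows the same rule; no fault in the chart is claimed.

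The cost is one revised clause, a re-issued hand-out and a short note to sites. Step 14 and the statistical analysis need no change on this account.
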